3.8 Study Size

Sample size is based upon an acceptable margin of error defined as less than 20% in the population of interest, with a significance level of < 0.05, and a correct response distribution to a knowledge-based question of 85%. This is anticipated to yield between 148 and 158 HCPs, and 148 to 158 patients participating, once the final evaluation has been completed.

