3.9 Data Analysis

Descriptive statistics for discontinuous data will be used to examine the key research questions of interest. The data for the overall population will be examined by users and non-users, general psychiatrists, child / adolescent psychiatrists, nurses, pharmacists, patients and caregivers, and individual countries. The data will be presented with responses' frequency distributions and 95% confidence intervals.

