HCPs will be expected to complete the surveys within one month of being recruited. Patient and caregiver recruitment will occur through the HCPs. To ensure an unbiased sample, up to three patients / caregivers can be recruited through a single HCP. It is, however, expected that most HCPs will recruit one or two patients / caregivers only. The prescribing physician will recruit consecutive patients / caregivers, and informed consent (via a letter provided as part of the recruitment process) will be taken once potential participants are randomly selected from the HCP lists submitted to PW. Assent will be taken from paediatric patients who are not old enough to give informed consent, and appropriate consent will be taken from parents / carers, as appropriate.

In order to minimise bias of selecting compliant patients, PW will randomly identify actual participants from lists of patients supplied by HCPs. A similar quota based methodology as used in HCP selection will be employed when recruiting patients and caregivers (e.g. recruitment continues until the target quota has been reached or exceeded). Patients and caregivers will be provided with an invitation letter (containing informed consent, and details of the survey and how to participate) through their HCP. The HCP will pass contact details of those patients and caregivers agreeing to take part to PW who will provide unique IDs and the web-link to a patient survey).

The Patient / Caregiver surveys will be answered either whilst the patient is still receiving ABILIFY® or within 2 months of receiving their last dose (this is to reduce risks of patients / carers not being able to recall aspects of treatment and use of the RM tools), and within 1 month of being recruited.

Question 3 in the Patient / carer survey asks how long the patient was treated for, and if they are still being treated. Question 2 asks how old the patient was at treatment initiation. PW will also administer the web questionnaires and collect results from the patients and caregivers.

A total sample size of 148 to 158 HCPs and 148 to 158 patients / caregivers, as discussed below, will be met.

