8.5 Study Size

The sample size will be driven by the estimated size of the population receiving ABILIFY[®] for the adolescent bipolar I mania indication. The sample size is based on an acceptable margin of error of less than 20% in the population of interest. This will yield between 148 to 158 HCPs and 148 to 158 patients / caregivers once the final evaluation has been completed.

The calculation to determine sample size was performed using a sample size calculator available from Raosoft⁽⁶⁾, and incorporated margins of error by country; hence, the range of 148 to 158 HCPs and 148 to 158 patients / caregivers. The calculation of sample sizes is described in Section 9.7.2.

To achieve a representative population of HCPs relevant to the local clinical practice of the country (e.g. nurses, ancillary HCPs and prescribers), and patients and caregivers, and to attain the ranges outlined above, approximately 20 to 30% of the actually prescribing / treating HCP

population would need to be invited as part of the recruiting process. For example, in the UK (estimated HCP population of 2188), a confidence level of 95% and 85% of correct responses to a knowledge based question, and a sample size of 13 HCPs, gives a margin of error of 19.36% (see Table 9).

It should be noted that ABILIFY[®] used in this indication is considered an area of specialised medicine. It is expected that some countries will have few prescribers, especially so since the product will not be actively promoted for use in the paediatric / adolescent population. The actual numbers surveyed will depend on the specific numbers of centres and HCP users. These values may be adjusted accordingly if there are particularly high or low national usages of ABILIFY[®] for the adolescent bipolar I mania indication at the time of the survey.

The following numbers of HCPs, and Patients or carers will be included per country:

UK	13 HCPs and 13 Patients / caregivers
Germany	13 HCPs and 13 Patients / caregivers
Spain	13 HCPs and 13 Patients / caregivers
Italy	13 HCPs and 13 Patients / caregivers
Sweden	13 HCPs and 13 Patients / caregivers
Denmark	13 HCPs and 13 Patients / caregivers
Norway	12 HCPs and 12 Patients / caregivers
Ireland	12 HCPs and 12 Patients / caregivers
Austria	12 HCPs and 12 Patients / caregivers
Portugal	12 HCPs and 12 Patients / caregivers
Cyprus/Greece	12 HCPs and 12 Patients / caregivers
Slovenia	12 HCPs and 12 Patients / caregivers

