8.6 Limitations of the Research Methods

Limitations include:

- Sampling bias of HCPs and patients (although measures are being put in place to minimise this).
- Participation bias (HCPs and patients or caregivers who volunteer to take part might be more likely to be interested in the product and RM), sampling will minimise bias owing to differential participation of different HCP types.

- Behaviour is being indirectly evaluated (as distinct from real-world behaviour).
- Survey is not relating use of tools to actual outcomes.
- It is not possible (for both ethical and practical reasons) to introduce a control (no exposure to RM tool) group, as RM tools must be universally offered in all countries as part of market authorisation.
- The level of education provided by different HCPs to patients / caregivers will affect how these answer survey questions it will not be possible to stratify patient / carer responses by HCP type (e.g. some child psychiatrists may provide excellent education whilst others do not). The survey will not link the patient / carer to their HCP.
- Social desirability bias (SDB), although potentially present in sample questionnaire
 studies, will be limited by avoiding direct interviewer questionnaires, by wording the
 introduction to emphasise that there are no "correct" answers, the measurement of
 behavioural choice rather than simply thinking, and also wording pre-ambles and
 question stems appropriately, to avoid any risk of inference as to "desirable" response.

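### The 148 to 158 is given as patients in section 3.8 but covers patients and caregivers combined, so the below-20% country margin fits only the combined group; dropping the HCP link leaves modest clustering unadjusted

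*Protocol*

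**What the plan says.** **Size.** Section 3.8 of the protocol expects "148 to 158 patients participating, once the final evaluation has been completed". Section 8.5 expects "148 to 158 patients / caregivers once the final evaluation has been completed", and section 8.2.2 gives the same combined total. Section 8.5 then sets one quota per country for patients and caregivers together: 13 in six countries and 12 in the other six, with no division between the groups.

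**Precision.** Section 3.8 states: "Sample size is based upon an acceptable margin of error defined as less than 20% in the population of interest", with 95% confidence and 85% correct answers. Section 8.5 says that margins by country produced the totals. Its only worked example is for HCPs: 13 out of 2,188 in the UK, with a margin of 19.36%.

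**Surveys and reporting.** Section 8.1 describes three surveys. The patient and caregiver questionnaires are separate annexes (2 and 3) with different question numbering. Section 3.9 will examine the data by users and non-users, "general psychiatrists, child / adolescent psychiatrists, nurses, pharmacists, patients and caregivers, and individual countries", with 95% confidence intervals.

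**Recruitment through HCPs.** Section 8.2.2 says "To ensure an unbiased sample, up to three patients / caregivers can be recruited through a single HCP" and expects one or two from most HCPs. Section 8.6 says that differences in the education given by HCPs will influence how patients and caregivers answer, and adds: "The survey will not link the patient / carer to their HCP".

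**The concern.** A reader of the abstract expects about 150 patients. The body promises about 150 respondents to two different questionnaires, so either survey may receive only half of that. A margin worked out for 12 or 13 respondents to one survey does not carry over to each of two surveys that share those 12 or 13.

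The margin formula also assumes independent respondents. Several respondents may come from one HCP, and the protocol itself names the reason why their answers would be alike. A cap of three limits the size of a cluster; it does not remove the correlation, which affects precision rather than bias. Leaving the HCP out of the survey record is a data-capture rule. A later analysis plan cannot compute a cluster-adjusted interval from a file that lacks the cluster identifier.

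At stake are the number of patients the study is understood to deliver, the precision claimed for patient and caregiver results within a country, and the honesty of the interval widths reported to the regulator.

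**Working it through.** **Inputs**
- Proportion correct p = 0.85, margin below 20 points, 95% confidence: section 3.8.
- UK example, n = 13 HCPs and N = 2,188: section 8.5.
- Country quotas of 13 (six countries) and 12 (six countries): section 8.5.
- Cluster size m of at most three, mostly one or two: section 8.2.2.
- Even split between patients and caregivers: assumed, as no split is given.
- Intraclass correlation (ICC) of 0.1 to 0.3: assumed. Section 8.6 implies only that it is positive.

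**Step 1. Reproduce the plan's figures.** Margin = 1.96 × √[p(1−p)/n × (N−n)/(N−1)] = 1.96 × √[0.1275/13 × 2175/2187] = 19.36 points, as stated. Without the finite population correction it is 19.41. The quotas sum to 6 × 13 + 6 × 12 = 150, inside 148 to 158.

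For 12 respondents the margin is 20.2 points without the correction. It falls below 20 only where the country population is 551 or less.

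**Step 2. One quota, two surveys.** The smallest n for a margin below 20 points, without the correction, is 1.96² × 0.1275 / 0.20² = 12.24, so 13. No division of 12 or 13 gives 13 to both surveys. With an even split:
- n = 7: 1.96 × √(0.1275/7) = 26.5 points
- n = 6: 1.96 × √(0.1275/6) = 28.6 points
- pooled over countries, n = 150/2 = 75: 1.96 × √(0.1275/75) = 8.1 points

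Patient population sizes are not visible. The correction would bring n = 7 under 20 points only in a country with about 15 eligible people or fewer.

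**Step 3. Clustering.** Design effect = 1 + (m − 1) × ICC, and the margin is multiplied by its square root.

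| m | ICC | Design effect | n = 13 | n = 150 pooled |
|---|---|---|---|---|
| 1 | any | 1.00 | 19.4 | 5.7 |
| 1.5 | 0.1 | 1.05 | 19.9 | 5.9 |
| 1.5 | 0.2 | 1.10 | 20.4 | 6.0 |
| 2 | 0.2 | 1.20 | 21.3 | 6.3 |
| 2 | 0.3 | 1.30 | 22.1 | 6.5 |
| 3 | 0.3 | 1.60 | 24.6 | 7.2 |

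At m = 1.5 and ICC 0.2 the interval is √1.10 = 1.049 times as wide, about 5% more. With unequal clusters, m is the respondent-weighted mean. For example, if 40% of HCPs supply one respondent, 40% two and 20% three, m = 3.8/1.8 = 2.1 and the design effect at ICC 0.2 is 1.22.

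**Step 4. Is the link available?** Under section 8.2.2 HCPs send the survey contractor lists of patients and pass on contact details, and the contractor issues the unique identifiers. Section 9.2 has the contractor hold the key between code and identity in a separate system. The HCP is therefore known at recruitment and is left out only of the survey record.

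**The case against.** **Hidden text.** The full data analysis section, Table 9 and the section cited for the sample-size calculation are not in the public text, and an interval formula is commonly left to the analysis plan. A split or an adjustment may be stated there. This stands as a limit on what can be said about the planned intervals. It changes neither the combined quota, which no split can make adequate for both surveys at country level, nor the rule that the survey record carries no HCP link.

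**No promise for patients alone within a country.** Section 3.9 lists respondent type and country as breakdowns but does not cross them. Table 7 has a single column for patients and caregivers, and their risk-knowledge questions run in parallel. A reader might infer that the plan guarantees a margin below 20% for patients alone in each country and fails to deliver it. The documents do not say that. What stands is that the country margin can refer only to the combined group, and that the protocol should say so.

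**Clustering is small.** The quotas are equal, about one patient or caregiver per HCP overall, and most HCPs are expected to recruit one or two. A reader might take three per HCP and a high ICC as typical and conclude that precision collapses. Three is a cap, and no ICC is given. The effect is modest on the cluster sizes the protocol expects.

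**The correction is not impossible.** The contractor holds the key, so the link might be rebuilt later. That is true, and it is also why carrying a code from the start is easy.

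**Limited consequence.** The visible plan is descriptive, with no test or pass threshold. This is fair, and it argues for a proportionate repair.

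**Conclusion.** The concern holds in a limited form. Sections 3.8 and 8.5 contradict each other on what the 148 to 158 counts; this needs no assumption. One quota of 12 or 13 per country serves two questionnaires, so the margin below 20% does not extend to either survey alone within a country. The 26 to 29 points shown there rest on an assumed even split and no finite population correction. Pooled over countries, each survey keeps about 8 points, so overall results by respondent type are not threatened.

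The clustering point is secondary. Its direction follows from section 8.6; its size rests on an assumed ICC. About 5% wider is the central illustration, and more only if clusters or the ICC are larger.

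Two further inferences are not supported. The plan's arithmetic is not wrong: 19.36% and a total of 150 both reproduce, and the fault lies in what the calculation is applied to. Nor do the documents describe a patient and that patient's own caregiver both filling places in the quota. Nothing visible excludes it, so it is a possibility to provide for and not a stated error.

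**What to change.** 1. In section 3.8, change the total to patients and caregivers combined, in line with sections 8.2.2 and 8.5.
2. In section 8.5, state that the country margin below 20% refers to the combined group. Give the expected number and the pooled precision for the patient survey and the caregiver survey separately.
3. Replace the no-link rule in section 8.6. Have the contractor attach an anonymous HCP code to each patient or caregiver record, and a family code where a patient and that patient's own caregiver both respond. This must be in place before data collection starts.
4. Compute cluster-robust 95% confidence intervals for patient and caregiver results.
5. In section 8.2.2, describe the cap of three as a limit on cluster size, not as a guarantee of an unbiased sample.

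The cost is one coded HCP field (plus the family code where it applies), a line on privacy in section 9.2 and the consent letter, and slightly wider intervals. No extra enrolment is needed.

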8.3 Variables

Variables of interest and their definition include:

• Age of patient

Defined as the age of the patient at treatment initiation

Dose

Defined as the most recent dose taken before completing the survey

• Treatment duration

Defined as the length of time since the first dose taken for this indication, irrespective of whether treatment is continuous or interrupted

• HCPs' experience using ABILIFY® for the adolescent bipolar I mania indication
Defined as how many the HCP has treated with ABILIFY® for moderate to severe manic
episodes in bipolar I disorder in adolescents aged 13 years and older

• Usage of tools

Defined as whether the respondent has used the RM tools on one or more occasions

• Medical specialty

Defined as: psychiatrist, child / adolescent psychiatrist, nurse or prescriber

• Country

Country where the HCP or patient / caregiver resides

The key survey effectiveness evaluation metrics are shown in Table 7. Questions designed to measure: demographics, awareness and distribution, use and utility, knowledge of tool content, knowledge of identified or potential risks of concern and behaviours are described in Section 9.1.1.

ABILIFY®

Table 7: Key effectiveness evaluation metrics

_	Target Audience	
Metrics	НСР	Patient / Caregiver
Awareness of tools	X	X
Utilisation of tools	X	X
Knowledge and comprehension		
Symptoms requiring physician notification	X	X
Recommended age	X	N/A
Indicated dose	X	N/A
Indicated treatment duration	X	X
Risks of		
• EPS	X	X
 Weight gain 	X	X
 Somnolence 	X	X
• Fatigue	X	X
Ability to respond correctly to hypothetical	X	X
risk scenarios		
Behaviour		
Reviewing safety information with	X	
Patients / Caregivers		
Monitor for ARs and appropriate action if	X	
ADR is identified		
Distribution of Patient information	X	X
brochure to Patients / Caregivers		
Educating Patients / caregivers about	X	X
symptoms of EPS, weight gain,		
somnolence and fatigue and need to report		
them to a physician		

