9.1.2 Informed Consent

As part of the recruitment process, HCPs will be asked to encourage patients and carers to participate in the patient and carer surveys. HCPs will be given letters to give to the Patient / carer that contain an informed consent section. This section describes:

- 1. Why patients / carers are being invited,
- 2. What the survey aims to ascertain,
- 3. The duration of the survey,
- 4. How the data will be aggregated and anonymised, and
- 5. How personal data will be respected and protected (and how survey participants' identities will be protected through the use of unique identifiers).

Since the indicated patients are adolescents (aged between 13 and 17), parental / guardian consent will be required before patients are surveyed.

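### The sampling unit for the patient and caregiver surveys is inconsistent, and nothing shown stops one adolescent's age and treatment duration from being counted twice in pooled or by-country figures

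*Protocol*

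**What the plan says.** Recruitment is described in Protocol Section 8.2.2. The paragraph on the HCP honorarium has HCPs supplying lists that name patients or caregivers, from which participants are randomised. The later paragraph on avoiding selection of compliant patients has the survey contractor drawing from lists of patients only. It then states that "Patients and caregivers will be provided with an invitation letter". Up to three patients or caregivers may come from one HCP.

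The targets are joint. Section 8.5 gives each of six countries "13 HCPs and 13 Patients / caregivers" and each of the other six 12 and 12, introduced by a sentence that speaks of patients or carers. Section 3.8 mentions patients only. Section 8.2.4 lists exclusions for HCPs and none for patients or caregivers.

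Section 8.2.2 says the patient/carer survey asks the patient's age at treatment start (Question 2) and how long the patient was treated (Question 3). Section 8.3 confirms the age variable: "Defined as the age of the patient at treatment initiation". Section 7.2.1 uses the ages of patients in this survey to judge whether the minimum age is respected, which is part of primary endpoint 4 in Section 8.1.

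On identification, Sections 8.2.2 and 8.4 describe codes issued to each participant, and Section 8.4 restricts the identity data to checking whether a survey was completed. Section 8.6 says that patients and carers will not be linked to their HCP. No link between a patient and that patient's caregiver is described.

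**The concern.** Age at initiation and treatment duration are facts about a patient, not about the person who reports them. If an adolescent and a parent both complete a survey, two records carry one fact. With a joint target and joint columns for patients and caregivers in Tables 5 and 7, and with results also examined by country (Section 3.9), a combined table would give that adolescent double weight. Its confidence interval would treat the two records as independent.

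The minimum-age check is the most exposed item, because it rests on few records per country and the event of interest should be rare. As an illustration only: if a country has 13 records and one under-age patient is reported by both members of a pair, the table reads 2/13 = 15%, when the patients behind it give 1/12 = 8%.

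An analysis plan cannot easily repair this afterwards. Pairs can be counted once only if they can be recognised, and that depends on how codes are issued and what use of the identity data is permitted. Both are settled before data collection.

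**Working it through.** **1. The plan's own figure.** Section 8.5 uses "a confidence level of 95% and 85% of correct responses to a knowledge based question", takes a UK pool of N = 2188, and states that "a sample size of 13 HCPs, gives a margin of error of 19.36" per cent. With E = z × √(p(1−p)/n) × √((N−n)/(N−1)), z = 1.96, p = 0.85, n = 13:

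- √(0.1275/13) = 0.0990, and times 1.96 gives 0.1941
- finite-population factor √(2175/2187) = 0.9973
- E = 19.36%, which reproduces the stated value.

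The criterion is "an acceptable margin of error of less than 20% in the population of interest". Country targets sum to 6 × 13 + 6 × 12 = 150, inside 148 to 158.

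**2. Effect of pairs.** Let f be the share of patient/caregiver respondents who belong to a patient-caregiver pair. The protocol does not give f, so a range is assumed. Both members of a pair are taken to report the same fact (correlation 1).

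- Distinct patients: D = n(1 − f/2).
- A patient in a pair has weight 2 and any other patient has weight 1. The variance is therefore proportional to [n(1−f) × 1 + (nf/2) × 4]/n² = (1+f)/n, so the effective size is n/(1+f).
- Margin = 1.96 × √(0.1275(1+f)/n). No finite-population factor is used, because the shown text gives no patient pool by country.

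| f (assumed) | n = 13: patients, effective n, margin | n = 12: patients, effective n, margin | n = 150: patients, effective n, margin |
|---|---|---|---|
| 0% | 13, 13, 19.4% | 12, 12, 20.2% | 150, 150, 5.7% |
| 25% | 11.4, 10.4, 21.7% | 10.5, 9.6, 22.6% | 131.25, 120, 6.4% |
| 50% | 9.75, 8.67, 23.8% | 9, 8, 24.7% | 112.5, 100, 7.0% |
| 100% | 6.5, 6.5, 27.5% | 6, 6, 28.6% | 75, 75, 8.1% |

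An analysis that ignored the pairs would report the 0% row whatever f was. The p of 0.85 is the plan's value for a knowledge question and serves here only to put the result on the plan's scale. The relative widening, √(1+f), does not depend on p: 12% at f = 25%, 22% at 50%, 41% at 100%.

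**3. How large can f plausibly be?** The targets are 150 HCPs and 150 patients/caregivers, so 150/150 = 1 respondent per HCP on average, and Section 8.2.2 expects most HCPs to recruit one or two. An HCP who contributes one respondent ordinarily contributes no pair. With a cap of three, an HCP can contribute at most one complete pair. Full pairing would therefore need one pair from each of 75 HCPs and nobody from the other 75. The 100% row is a bound and not a forecast.

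**The case against.** The strongest reply is that double counting requires pooling, and pooling is not established. Patients and caregivers have separate questionnaires with their own item numbers, and Section 3.9 names both among the groups by which results are examined. In a table of either group alone, pairing repeats no patient. The data management and analysis sections and the annexes are withheld, so a rule for pairs may exist there. This limits the point to pooled and by-country figures, but it does not remove it: the recruitment, exclusion and ID sections are shown and contain no such rule.

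Some of the wording also fits one respondent per patient: lists of patients in Section 8.2.2, patients or carers in Section 8.5, patients alone in Section 3.8. None of these states it, and the honorarium paragraph of Section 8.2.2 reads otherwise.

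The contractor holds contact details and, under Section 9.2, a restricted key from codes to patient identities, so it might be able to recognise a pair. But no rule tells it to, and the limit on use in Section 8.4 would not cover it.

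Three stronger readings are tempting and are not supported:

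- A reader might infer that the parent is always a second respondent, because Section 9.1.2 says "parental / guardian consent will be required before patients are surveyed". Giving consent is not being listed, drawn and surveyed.
- A reader might infer that the brochure questions are double-counted too. Table 2 classes them as awareness and distribution, and awareness belongs to each respondent. The question wording is withheld.
- A reader might infer that the survey really covers about 75 patients. That needs full pairing, which step 3 of the working shows to be implausible.

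**Conclusion.** The point holds in a limited form. The protocol does not define one sampling unit for the patient and caregiver surveys, and the sections shown would allow both members of a pair to be counted without being recognisable as a pair. The consequence is conditional: it arises only if both members are drawn and reply, only in pooled or by-country figures, and only for age at initiation and treatment duration. Knowledge and behaviour answers from two people are separate responses, though probably correlated.

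The size depends on an unknown pairing rate. At an assumed 25%, the country margin for patient facts is 21.7% to 22.6% instead of 19.4% to 20.2%, which takes 13-record countries over the plan's 20% limit. (Twelve records already sit marginally above it without a finite-population factor.) The total across countries is little affected at that rate: 6.4% instead of 5.7%. The minimum-age check is also only partly exposed, since Table 5 calls the patient-reported age an indirect aid and the HCP survey has its own age item. This is a cheap improvement to make before recruitment, not a flaw that undermines the study.

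**What to change.** 1. Reconcile Sections 3.8, 8.2.2 and 8.5 so that the treated patient is the sampling unit and HCPs list patients.
2. Allow patient-caregiver pairs, but give both members the same patient number in the ID scheme, with a suffix for who is answering.
3. Extend the permitted use of the ID data in Section 8.4 to cover this link. It need not identify the HCP, so the commitment in Section 8.6 is kept.
4. In any pooled or by-country table, count age at initiation and treatment duration once per patient, and state the number of distinct patients beside the number of respondents.

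The cost is a few sentences, one extra ID field, and a slightly smaller denominator for those two items. Counting once is also more precise than leaving duplicates in and widening the interval. At 25% pairing in a 13-record country, 1.96 × √(0.1275/11.375) = 20.8%, against 21.7%. At 50%, 1.96 × √(0.1275/9.75) = 22.4%, against 23.8%.

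Keeping pairs is preferable to admitting only one respondent per patient. Section 8.2.2 expects the pool of treating HCPs to be small, and a one-respondent rule would lose households where only the other member is willing to answer.
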